12.4 Safety Evaluation and Analysis

Safety analysis will be conducted on the full analysis set. All AEs occurring on study will be listed by subject in a data listing. The type of adverse events (AEs), severity, and incidence rates will be presented in all treated subjects. Comparison of the frequency of adverse events (for example, percentage of patients with worst toxicity grade 2 or higher) will be conducted using chisquare or Fisher exact tests.

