6.0 DURATION OF TREATMENT

Therapy with enzalutamide or enzalutamide/mifepristone will continue until one of the following events occurs.

1. Progression of disease according to 2008 PSAWG-2 criteria⁴⁷ is met (Appendix C, D). Note-PSA progression (or response) will not be assessed until the patients' first 12-week disease assessment visit.
2. Unacceptable toxicity is encountered.
3. Patient withdraws consent
4. Patient is withdrawn from study at the discretion of the investigator

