10.0 SAFETY

10.1 Adverse Events

An adverse event (AE) is any untoward medical occurrence in a patient or clinical investigation of a subject who has been enrolled in a clinical study and who may have been administered an investigational product, regardless of whether or not the event is assessed as related to the study drug treatment. An AE can therefore be any unfavorable and unintended sign (including an abnormal laboratory finding), symptom, or disease temporally associated with the use of an investigational product, regardless of whether or not the event is assessed as related to the investigational product. Abnormal laboratory values, ECG findings, or vital signs that are considered clinically significant by the investigator, and pre-existing medical conditions that worsen during a study, should be recorded as AEs.

For the purpose of data collection, all AEs that occur after initiation of study drug through 30 days after last dose of study treatment (or until a subject is determined to be a screening failure) are to be recorded by the investigational site. This requirement includes AEs from unscheduled as well as scheduled visits.

Assessment of toxicities and adverse events will be graded according to the Common Toxicity Criteria (CTC), version 4.03:

- V4.03 (CTCAE): publish date June 14, 2010:
http://evs.nci.nih.gov/ftp1/CTCAE/CTCAE_4.03_2010-06-14_QuickReference_8.5x11.pdf

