10.8.3 Follow-Up of Adverse Events

Any SAE or AE assessed as possibly related that led to treatment discontinuation (including clinically significant abnormal laboratory values that meet these criteria) and is ongoing 30 days after last dose of study treatment must be followed until either resolution of the event or determination by the investigator that the event has become stable or irreversible. This follow-up guidance also applies to possibly-related serious adverse events that occur *greater than 30 days after last dose* of study treatment. The status of all other continuing adverse events will be documented as of 30 days after last dose of study treatment.

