size of 84 patients (42/arm) is required, using a one-sided test at the $\alpha=0.10$ significance level. This assumes a two-year accrual period and a subsequent one-year follow-up period. Kaplan-Meier⁴¹ curves will be generated and the two treatment arms compared using a logrank test. Median time to event in each group will be estimated along with 90% confidence intervals using the method of Brookmeyer and Crowley⁴². Cox⁴³ proportional hazards regression models will be fit to assess and adjust for the effects of baseline covariates. Overall survival and radiographic progression-free survival will be analyzed similarly. The relative PSA change within each arm will also be reported using a waterfall plot according to working group recommendations for phase II studies in CRPC, as a secondary endpoint⁴⁴. Adverse events will be summarized by grade and type and compared between groups using chi-square or Fisher's exact tests.

For the secondary endocrine PD endpoint, we will compare endocrine PD marker differences between the enzalutamide alone versus the Enzalutamide + Mif treatment arms. In previous placebo controlled trials of Mif, serum cortisol levels reliably doubled from a baseline of approximately 15 $\mu\text{g}/\text{dL}$ to $>30 \mu\text{g}/\text{dL}$ after treatment with mifepristone^{38,39}. Based on the reported interquartile ranges, and assuming normality of the distribution, the coefficient of variation is estimated at 50%. An interim futility analysis will be conducted after half (35) of the expected 70 PSA events are observed. At this stage we will conduct an interim analysis of the difference in cortisol levels; a lack of biomarker effect would provide justification for closing the trial. Thus, assuming a true mean for the control arm of 15 and standard deviation of 7.5 on day 29 post randomization, our sample size will provide 90% power to detect a difference of 15 vs. 22 $\mu\text{g}/\text{dL}$ between the two treatment arms, based on t-test at a two-sided alpha level of 0.05. This calculation allows for a 15% missing data rate prior to day 29 post randomization. The other endocrine laboratories collected at day 29, will be similarly compared between treatment groups.

In addition, if at the interim analysis the conditional power for the primary PSA endpoint is $<25\%$, we will consider terminating the trial for futility. This stopping rule will provide minimal power loss ($<3\%$)⁴⁴.

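### The between-arm AE comparison uses crude percentages although observation time depends on when treatment stops, so if the plan's own effect is real Arm 2 shows about 5 to 10 points of excess from longer observation alone

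*Combined protocol and SAP*

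**What the plan says.** Four sections of the combined protocol and SAP bear on this.

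- **Collection (10.1).** The sites record "all AEs that occur after initiation of study drug through 30 days after last dose of study treatment". Section 10.8.3 adds to this: "This follow-up guidance also applies to possibly-related serious adverse events that occur" more than 30 days after last dose. Late, possibly related SAEs are therefore not lost, but routine AE recording ends at 30 days.
- **Duration (6.0).** "Therapy with enzalutamide or enzalutamide/mifepristone will continue until one of the following events occurs". The list is progression, toxicity ("Unacceptable toxicity is encountered"), withdrawal of consent and investigator decision. PSA progression is not judged before the first 12-week disease assessment.
- **Analysis (13.1).** "Adverse events will be summarized by grade and type and compared between groups using chi-square" or Fisher's exact tests.
- **Analysis (12.4, printed after 13.3).** The compared quantity is illustrated by the "percentage of patients with worst toxicity grade 2 or higher". The section also says that "incidence rates will be presented in all treated subjects", but defines no person-time denominator.

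No section plans a common comparison window, a time-to-first-AE analysis, an exposure-adjusted rate or a summary of treatment duration by arm.

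**The concern.** A crude percentage of patients ever having an event grows with the time each patient is watched. Here the watching stops 30 days after drug stops, and drug stops mainly at progression, which is what the trial hopes to delay in Arm 2 (enzalutamide plus mifepristone). A trial that succeeds on its primary endpoint therefore observes Arm 2 for longer and, at the same underlying AE rate, counts more Arm 2 patients with an event.

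At stake is the only randomised tolerability comparison in the programme. Section 1.9 itself warns that the combination could bring toxicity nobody anticipated. A reader of the planned table could not separate more toxic treatment from longer treatment, because treatment duration by arm is not reported beside it.

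**Working it through.** **1. The plan's own figures.** Section 13.1 gives HR 0.60, medians of 24 and 40 weeks (24/0.60 = 40), one-sided alpha 0.10, 80% power, 42 per arm, 70 expected events, two years of accrual and one further year of follow-up.

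- Schoenfeld: 4 × (1.2816 + 0.8416)² / (ln 0.60)² = 69.1, so 70 events, as stated.
- With exponential times, 104 weeks of uniform accrual and 52 weeks of follow-up, the event probabilities are 0.930 and 0.812 (mean 0.871).
- Freedman's formula gives 73 events, and 73/0.871 = 83.8, so 84 patients, as stated.

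The design medians can therefore be used as the plan's own alternative.

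**2. Simplest version.** Let time on treatment be exponential with μ = ln 2/median, let the first-AE hazard λ be constant and equal in both arms, and let observation run 30/7 weeks past last dose. Then

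P(AE) = 1 − exp(−λ × 30/7) × μ/(μ + λ).

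At λ = 1/52 per week this is 44.7% (24 weeks) and 56.4% (40 weeks), a gap of 11.6 points before rounding. It is too large for two reasons. It ignores the end of follow-up, and it lets 1 − 2^(−12/24) = 29% of control patients stop before week 12, when PSA progression is not yet assessed.

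**3. With the end of follow-up and the 12-week rule.** Let S_Y(x) be the probability that the patient-specific window is still open at week x: 1 up to 12 + 30/7 weeks, then exp(−μ(x − 30/7)). Let S_C(x) be the probability of not yet being cut off: 1 to week 52, then (156 − x)/104. Then

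P(AE) = ∫ λ exp(−λx) S_Y(x) S_C(x) dx over 0 to 156 weeks, and mean observation = ∫ S_Y(x) S_C(x) dx.

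- Mean observation is 38.0 versus 51.5 weeks, ratio 1.35. Without the 12-week minimum it is 36.1 versus 50.3, ratio 1.39.

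| AE hazard per patient-year (assumed, equal in both arms) | Arm 1 | Arm 2 | Gap (points) | Gap without 12-week minimum |
|---|---|---|---|---|
| 0.25 | 16.1% | 21.0% | 4.9 | 5.2 |
| 0.5 | 28.7% | 36.1% | 7.4 | 8.0 |
| 1 | 46.8% | 55.9% | 9.1 | 10.2 |
| 2 | 67.9% | 75.8% | 7.9 | 9.6 |

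The gap is about 5 to 10 points with no difference in AE rate.

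**4. Size against noise.** At 46.8% and 55.9% with 42 per arm, the standard error of the difference is √[(0.468 × 0.532 + 0.559 × 0.441)/42] = 0.109. The 9.1-point shift is less than one standard error. Taking a two-sided 0.05 level (assumed; the plan sets none for AEs), 12-week AE risks of 5% to 30% and the 12-week minimum, chi-square would declare a difference in about 9% to 16% of trials, against 5% to 6% with equal observation.

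**5. After the fix.** At 1 per patient-year, the 12-week cumulative risk is 1 − exp(−12/52) = 20.6% in both arms, and the rate is 1 per patient-year in both, so the artefact disappears under these assumptions.

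**The case against.** The case for leaving the plan alone has real content.

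- **The gap is conditional.** It needs the hypothesised effect to be true, PSA-PFS to track time on treatment, and AEs that keep arising. Section 9.9 puts rash (about 30% of patients) mostly in the first two weeks, and Section 5.2 says most dose-limiting toxicity in earlier enzalutamide work came within six weeks. Such events are barely affected. This stands and limits the point.
- **Cumulative risk over a course of treatment is a legitimate quantity.** Patients treated longer do have more AEs. That also stands. The difficulty arises only when the difference is read as greater toxicity, which is hard to avoid if duration is not shown.
- **The plan is not closed.** The percentage is given as an example, incidence rates are mentioned, and drug calendars and pill counts (Section 9.1) would supply exposure. This shows that the repair is cheap, not that it is planned.
- **No decision hangs on the test.** AE comparison is not a listed phase II objective, and safety is monitored weekly (Section 10.8.4). This keeps the point modest.

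Two stronger readings are tempting and should not be drawn. A reader might infer that crude percentages also hide toxicity when mifepristone drives patients off treatment. They do not: a patient who stops for toxicity already counts as having an event. Take a 1.5-fold AE hazard in Arm 2 (1.5/52 = 0.0288 per week) and a 12-week median on treatment caused by those AEs. The excess stopping hazard needed is ln 2/12 − ln 2/24 = 0.0289 per week, almost the same number. The formula in step 2 of the working, with μ = ln 2/24 for progression, then gives 55.8% against 44.7%, and the harm shows. Early stopping can hide only AEs other than the one that caused the stop. A reader might also infer that nothing is followed after 30 days; Section 10.8.3 says otherwise for possibly related SAEs.

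**Conclusion.** The point holds in a limited form. Under the plan's own alternative, the comparison in Sections 12.4 and 13.1 builds in an apparent Arm 2 excess of about 5 to 10 percentage points for AEs that continue to arise, with no difference in the underlying rate.

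This rests on four assumptions, because the documents give no AE rates: exponential time on treatment with the PSA-PFS medians, an equal and constant AE hazard of 0.25 to 2 per patient-year, uniform accrual, and stopping that is independent of the AE counted. If the arms stop at similar times, the artefact vanishes.

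For any single AE type the shift is smaller than chance variation at 42 per arm. It matters because it runs in one direction across AE types and a larger sample would not remove it. It does not touch the primary endpoint, the sample size or patient protection. It is a worthwhile, inexpensive improvement to the safety analysis rather than a flaw in the design.

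**What to change.** In Sections 12.4 and 13.1:

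1. Make the between-arm AE comparison over a common window, the first 12 weeks from first on-study treatment, using AEs already collected (on treatment plus 30 days). The study calendar has the same AE visits in both arms, and little PSA-driven stopping can fall inside this window.
2. For the whole study, report events per patient-year of observation and treatment duration by arm beside the crude percentages, so that the percentages can be read as cumulative risk over treatment courses of different length.
3. State how many patients in each arm stopped too early to have a complete window. With the 30-day tail these are patients stopping before about week 8 (12 − 30/7 = 7.7 weeks).

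The cost is SAP wording and two extra tables, with no new visits or data. There are two drawbacks to state. Rates per patient-year assume a roughly constant hazard and describe early-onset events such as rash poorly, and windows for very early stoppers will be slightly incomplete.

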1.8 Mifepristone

Mifepristone is a synthetically synthesized hormone receptor modulator derived from the naturally occurring material estrone. Mifepristone is a progesterone and glucocorticoid receptor (GR) antagonist currently FDA approved for emergency contraception and Cushing's disease. It is also known to be a potent inhibitor of the GR³⁶. While a single dose of mifepristone 200 mg combined with misoprostol is needed to terminate pregnancy,

potentially higher doses are required for potent anti-GR effects³⁷. Mifepristone is now FDA approved for the indication of Cushing's disease at daily doses ranging 300mg-1200mg (Korlym, Corcept). It is also being studied in patients without Cushing's disease for indications including hypercholesterolemia, weight gain, Alzheimer's and psychosis, and has been well tolerated at multiple different doses including ranging from 200-600mg daily³⁸⁻⁴⁰. With daily dosing, the most common side effects considered related to study drug include headache, dizziness, nausea/vomiting, constipation, fatigue, abdominal cramping, rash, and depression. In the study of Alzheimer's patients who were treated for 16-weeks with 300mg/day there were 4 severe adverse events (SAE's) in the 41 patients on the mifepristone arm 2 of which were considered potentially related to the study drug (rash/nausea/decreased appetite, seizure). Hypokalemia, likely due to mineralocorticoid excess, was observed more frequently in the mifepristone arm of the study than placebo, however there were no high grade hypokalemia events and no clinically serious consequences noted⁴⁰. The other adverse event related to mechanism of action (GR antagonism) is adrenal insufficiency. As of 2013 investigator brochure, with over 1400 subjects enrolled, only 7 cases of adrenal insufficiency have been documented, all in the studies for Cushing's disease. They were mild and treated with supplemental corticosteroids. Although a macular-papular rash with mifepristone is common, it is also typically mild and treated with topical agents, and does not typically recur or escalate with retreatment. Severe rash syndromes and/or adrenal crisis have not been observed⁴⁰.

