7.2 On Study Visits

On study visit will every 2 weeks through 8 weeks on study, then monthly. The frequency of visits early in the trial is to ensure adequate patient safety while on study.

For study visits, including day 1, the following full set of blood tests will need to be obtained: CBC, serum chemistries, LDH, PSA. In addition, as mifepristone can affect the hypothalamic-adrenal gland axis and to monitor for endocrine related adverse events, serum cortisol cortisol and thyrotropin will be assessed at day 1 and at the subsequent two monthly (day 29, 57) study visits. A second whole blood sample for circulating tumor cell correlative study will be performed on first day of study drug as described in Section 12.1. Other monthly assessments including ECOG status, concomitant medications etc. to be collected are outlined in the study calendar. To asses for potential QTc prolongation with the combination of study agents, a second EKG will be obtained after both medications at steady state. Note: monthly visits can occur ± 3 days of scheduled visit.

Disease assessment with imaging (as in pre-study evaluation) will be repeated every 12 weeks while on study, starting at first day of concomitant daily study drug administration.

7.2.1 Pharmacokinetics sampling:

Plasma samples to determine enzalutamide and M2 metabolite levels within the serum of patients on study will be collected and sent to Medivation Inc. for pharmacokinetic (PK) analysis. Patients should withhold enzalutamide administration prior to visits with PK sampling and should take enzalutamide after the PK sample is collected. The pre-dose PK sample should be taken immediately before enzalutamide administration. The PK sample should be collected even if patient did not withhold enzalutamide.

For the phase I study, the following samples will be collected for PK modeling before enzalutamide, mifepristone dose for each day. Samples will be taken weekly starting at day 29 for the next four weeks.

1. Day 29
2. Day 36
3. Day 43
4. Day 50
5. Day 57 (4 weeks after start of phase I daily concomitant dosing)

For patients in the Phase II portion of the study, PK's will be collected on day 1 of on-study period (steady-state enzalutamide alone) and after 4 weeks on study.

All samples will be shipped to:

[name], Sample Receiving
inVention Health Clinical Lab, Inc.
[name]
[name]
[contact]
[contact]
Email: [contact]

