9.4 Treatment Management of Hypertension

Hypertension may develop while on mifepristone due to excess mineralocorticoid activity due to treatment dependent increase in ACTH. Because of this, hypertension occurring secondary to mifepristone may be most effectively prevented through the concurrent administration of eplerenone which is capable of inhibiting mineralocorticoid induced hypertension. The following table provides a recommended algorithm for treatment-emergent hypertension management. Decisions to hold or decrease the dose of study treatment must be based on blood pressure (BP) readings confirmed with a second measurement at least 5 minutes after the first measurement.

BP Measurements – Systolic/Diastolic	Treatment/Dose Modification
> 140 mm Hg (systolic) and <160 mm Hg OR > 90 mm Hg (diastolic) and < 105 mm Hg OR	
• Add new or additional antihypertensive medications or increase dose of existing medications.• Maintain dose of study treatment.
≥ 160 mm Hg (systolic) OR ≥ 105 mm Hg (diastolic)	
• Hold mifepristone.• Add new or additional anti-hypertensive medications or increase dose of existing medications.• Monitor subject closely for hypotension (if on anti-hypertensive medications) until study treatment is restarted.• Resume treatment at same dose level when BP falls to < 140/90 mm Hg.

If toxicity occurs, hold study treatment, adjust or add medications to mitigate the toxicity. When resolved to \leq Grade 1, resume study treatment with first dose level reduction.

If toxicity recurs at the first dose level reduction, hold study treatment, adjust or add medications to mitigate the toxicity. When resolved to \leq Grade 1, resume study treatment with the second dose level reduction.

[Rest of Page Intentionally Left Blank for Formatting Purposes]

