9.6 Management of Hypokalemia

Hypokalemia may occur in patients treated with mifepristone due to mineralocorticoid excess and potentially. Initial management of hypokalemia should include oral K⁺ supplementation as well as the addition of eplerenone, as appropriate.

Serum K ⁺	Grade	Action	Further Action and/or Maintenance
<3.5mM-3.0mM	Grade 1	Initiate oral K ⁺ Supplements	Titrate K ⁺ dose to maintain serum K ⁺ $\geq 3.5\text{mM} \leq 5.0\text{mM}$ (Maintenance of pts at $\geq 4.0\text{mM}$ is recommended); weekly laboratory studies until K ⁺ $\geq 3.5\text{mM} \leq 5.0\text{mM}$.
<3.0mM-2.5mM	Grade 3	Withhold mifepristone and initiate IV K ⁺ and cardiac monitoring	Restart mifepristone at dose level -1; Titrate K ⁺ dose to maintain serum K ⁺ $\geq 3.5\text{mM} \leq 5.0\text{mM}$; weekly laboratory studies until K ⁺ $\geq 3.5\text{mM} \leq 5.0\text{mM}$.
<2.5mM	Grade 4	Withhold mifepristone and initiate IV K ⁺ and cardiac monitoring	Call study PI prior to re- initiating study treatment.

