10.8 Other Safety Considerations

10.8.1 Laboratory Data

All laboratory data obtained during the course of the study should be reviewed. Any abnormal value that leads to a change in subject management (e.g., dose reduction or delay, requirement for additional medication or monitoring) or is considered to be of clinical significance by the investigator should be reported as an adverse event or serious adverse event as appropriate, unless this value is consistent with the patient's present disease state or is consistent with values obtained prior to entry into the study.

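### Safety is compared between arms only as adverse-event frequencies, so the size of any potassium or blood-pressure shift is not estimated, although both are recorded at the same visits in both arms.

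*Combined protocol and SAP*

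**What the plan says.** Two places describe the between-arm safety analysis. Section 12.4 states that "The type of adverse events (AEs), severity, and incidence rates will be presented in all treated subjects" and then plans a comparison of frequencies, for example the "percentage of patients with worst toxicity grade 2 or higher) will be conducted using chisquare or Fisher exact tests". Section 13.1 says: "Adverse events will be summarized by grade and type and compared between groups using chi-square or Fisher's exact tests". Neither plans a by-arm summary of potassium or blood-pressure values, whether as change from baseline, shift table or worst value.

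The protocol gives reasons to look at both:

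- Section 1.8, on hypokalemia in a cited 16-week placebo-controlled study: it "was observed more frequently in the mifepristone arm of the study than placebo, however there were no high grade hypokalemia events".
- Section 9.6: "Hypokalemia may occur in patients treated with mifepristone due to mineralocorticoid excess".
- Section 9.4: "Hypertension may develop while on mifepristone due to excess mineralocorticoid activity".

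Both are measured. At study visits, section 7.2 says, "the following full set of blood tests will need to be obtained: CBC, serum chemistries, LDH, PSA". The section 8.0 calendar marks vital signs (including blood pressure) and serum chemistry (including K+) on Days 1, 15, 29, 43, 57 and then monthly, with no distinction by arm.

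Section 13.1 does compare some laboratory values as measurements, namely cortisol and the other endocrine tests at Day 29. The calendar footnote shows that these are TSH and AM cortisol. Potassium is not among them.

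**The concern.** An event count records that a threshold was crossed and that someone reported it. It does not give the size of a shift, and it does not register movement within the normal range.

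Reporting also passes through judgement. Under section 10.1, laboratory values and vital signs become adverse events when the investigator considers them clinically significant. Section 10.8.1 adds, for laboratory values, those that change management, or any value that "is considered to be of clinical significance by the investigator should be reported as an adverse event". The trial is open label, and sections 9.4 and 9.6 attribute hypertension and hypokalemia to mifepristone, so reporting could differ between arms in either direction. Recorded values at fixed visits are much less exposed to this.

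Phase I cannot supply the answer. It has no control arm, and section 5.2 counts only grade 3 or 4 events as dose limiting. Phase II is the only randomised look at lesser mineralocorticoid effects of the combination.

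**Working it through.** **1. Arm size, from section 13.1.** For HR 0.60, one-sided alpha 0.10 and 80% power, the events needed are 4(z₀.₉₀ + z₀.₈₀)² / (ln 0.60)² = 4(1.2816 + 0.8416)² / 0.2609 = 69.1, rounded up to 70, as stated. With 24 months' accrual, 12 months' follow-up and medians of 6 and 10 months, event probabilities are about 0.92 and 0.79. That gives 82-83 patients, close to the planned 84. So there are 42 per arm. With the 15% missing rate that section 13.1 allows for cortisol, 42 × 0.85 = 35.7, or about 36 per arm at Day 29.

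**2. Assumed inputs.** The documents give no mean, SD or event rate for potassium or blood pressure, and no alpha for the adverse-event tests. I assume control potassium 4.2 mM, SD 0.35-0.5, a true fall of 0.2-0.3 mM, within-patient correlation 0.5 and two-sided 5%, the level that section 13.1 uses for cortisol.

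**3. Day 29 potassium adjusted for Day 1 (ANCOVA).** SE = SD × √[(1 − 0.5²) × 2/36] = 0.204 × SD.

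- SD 0.5, fall 0.2: SE 0.102, ratio 1.96, power Φ(1.96 − 1.96) = 50%.
- SD 0.4, fall 0.3: SE 0.0816, ratio 3.67, power Φ(1.71) = 96%.
- SD 0.35, fall 0.3: SE 0.0714, ratio 4.20, power Φ(2.24) = 99%.

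Simulation gives 49%, 95% and 98%. The 95% interval has half-width 1.96 × 0.204 × SD = 0.40 × SD, that is 0.14-0.20 mM.

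**4. The event-count counterpart.** This is a Fisher test on worst potassium below 3.5 mM, 42 per arm, with every such value counted.

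| | ANCOVA, Day 29 | Fisher, worst value <3.5 mM |
|---|---|---|
| No supplement effect | 49-98% | 28-78% |
| Supplements add 0.5 mM after a value <3.5 mM | 37-91% | 32-77% |

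The Fisher column counts four visits (Days 15, 29, 43, 57). Counting a fifth on-study visit raises the upper end of the first row to about 82%. In the supplement row, a true 0.3 mM fall is estimated as about 0.25 mM.

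**5. Blood pressure, illustration only.** I assume systolic mean 132 mm Hg, SD 12-16, a rise of 8 mm Hg, 42 per arm, one visit and no adjustment. At SD 12 the ratio is 8 / (12 × √(2/42)) = 3.05. The comparison of means has 62-86% power, and a Fisher test on the share above 140 mm Hg has 37-59%. These figures ignore antihypertensive treatment and are not worst-over-study counts.

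**The case against.** The best defence is that the planned comparison is broader than its example suggests. Grade 2 or higher is only an illustration, and section 13.1 compares events by grade and type. For potassium, reporting is largely rule-driven: section 9.6 lists oral supplementation for values from 3.0 to below 3.5 mM, and section 10.8.1 asks for an event report whenever an abnormal value leads to additional medication or monitoring. This stands, and it is why the fair comparator above is a count below 3.5 mM with full reporting. Differential reporting between arms is possible but not shown.

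A reader might infer more: section 9.6 goes from Grade 1 to Grade 3, so a grade 2 or higher contrast would count only potassium below 3.0 mM and would have almost no power. The documents do not support that. Section 9.6 is a management table, section 10.1 says events are graded by CTCAE 4.03, and the plan does not adopt grade 2 as a fixed cut. A reader might also carry the absence of high-grade events over to blood pressure. Section 1.8 reports it for hypokalemia only, and section 9.4 gives no grade or rate.

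Treatment of low values also weakens the alternative. Simulating the SD 0.4, fall 0.3 mM case with supplements adding 0.5-0.7 mM lowers ANCOVA power from 95% to 70-81%, while the Fisher count stays at 76-78%. Most of the power advantage can therefore disappear. What remains is an estimate of size, with an interval, that does not depend on who completed an event form.

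Finally, this is an 84-patient phase II trial with no powered safety hypothesis. That argues for estimation rather than a further set of tests.

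**Conclusion.** The gap holds in a limited form. Low-grade events are within the planned comparison, and most potassium values below 3.5 mM should reach it. Not analysed are the size of any potassium or blood-pressure shift, change within the normal range, and values not judged significant in an open-label trial. The protocol itself names both effects as possible, records both in each arm, and already compares cortisol as a measurement.

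The gain is modest: 49-98% against 28-78% power without a supplement effect, and 37-91% against 32-77% with one. These ranges rest entirely on the assumed mean, SD, fall and correlation. The statement that the values are recorded but not analysed rests on the text alone. The primary analysis and sample size are unaffected.

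**What to change.** Add to section 12.4, for Phase II:

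- (a) The between-arm difference in potassium, systolic and diastolic blood pressure at Day 29 and Day 57, adjusted for the Day 1 value, with 95% confidence intervals and labelled as estimation.
- (b) Worst on-study potassium category by arm, including the proportion below 3.5 mM, derived from recorded laboratory values and not only from adverse-event forms.
- (c) Newly started potassium supplements, eplerenone and antihypertensives by arm, shown next to (a).

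The cost is SAP wording and a small amount of programming. The values and concomitant medications are already scheduled for collection in section 8.0, so no test, visit or patient is added and clinical management does not change. There is one small downside. Supplements and antihypertensives pull the means together, so (a) understates the untreated effect and must be read with (b) and (c).
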